10.2 LIST OF ANTICIPATED POTENTIAL ADVERSE EVENTS

Anticipated potential adverse events listed below include those that might reasonably be expected to occur in this study because they are associated with glaucoma, cataract surgery, ab-interno transluminal viscoelastic delivery, trabeculotomy, and/or the risk analysis for OMNI System. Adverse events may occur intra-operatively or post-operatively.

- Layered Hyphema $\geq 1\text{mm}$ (Microhyphema or Hyphema $<1\text{mm}$ is expected and will not be considered an AE)
- IOP increase $\geq 10\text{ mmHg}$ above baseline IOP at ≥ 1 month visit³³
- IOP increase requiring management with systemic medication at ≥ 1 month visit³²
- Need for secondary surgical intervention to manage IOP³²
- Hypotony (IOP $<6\text{ mmHg}$)³⁴ with at least one of the following conditions:
 - Flat anterior chamber requiring anterior chamber reformation
 - Corneal folds
 - Choroidal effusions requiring or undergoing surgical drainage
 - Suprachoroidal hemorrhage

³³ To avoid double counting an event, events of IOP $\geq 10\text{ mmHg}$ above baseline IOP at ≥ 1 month visit that require management with systemic medication or secondary surgical intervention should be reported as “IOP increase requiring management with systemic medication at ≥ 1 month visit” or “Need for secondary surgery intervention to manage IOP,” respectively.

³⁴ Hypotony is defined as “early” if it occurs within 2 weeks of surgery and “late” if it occurs more than 2 weeks after surgery

e) Maculopathy

- Corneal injury
- Corneal edema after 1 week
- Corneal abrasion
- BCVA loss of ≥ 10 letters (ETDRS) at or after 3 months postoperative
- Descemet's membrane tear or detachment
- Chronic anterior uveitis (inflammation of grade 1+ or worse persisting for more than 3 months post-operatively or that recurs less than three months after discontinuing treatment)
- Wound leak
- IOL dislocation and/or damage
- Intracorneal Hematoma
- Posterior capsular tear
- Pupillary block
- Cyclodialysis
- Iridodialysis or significant iris damage
- Peripheral Anterior Synechiae > 1 clock hour
- Suture abscess or other local infection
- Flat or shallow anterior chamber requiring anterior chamber reformation
- Aqueous misdirection
- Choroidal detachment
- Choroidal effusion requiring surgical drainage
- Choroidal hemorrhage
- Suprachoroidal hemorrhage
- Vitreous hemorrhage
- Perforation of sclera
- Clinically significant cystoid macular edema
- Retinal detachment
- Retinal tear
- Chronic pain present later than 3 months after the surgery
- Increase in C/D ratio of > 0.3 units compared to baseline on slit lamp exam
- TASS
- Endophthalmitis

10.3 REPORTING ADVERSE EVENTS AND UNANTICIPATED ADVERSE DEVICE EFFECTS

Identification, collection and reporting of adverse event information is the responsibility of the principal investigator. The investigator records the date of the event, its severity,

treatment (if any) and the assessed relationship of the event to the study device on the Adverse Event Case Report Form (AE CRF).

Any ocular-related **serious adverse event (SAE)** should be reported to the study sponsor within one working day of learning of the event. Non-ocular-related SAEs should be reported to the study sponsor within two working days of learning of the event. Email the AE CRF to [REDACTED]

Any **unanticipated adverse device effects (UADE)** must be reported to the following two entities:

1. The study sponsor – Within one working day of the investigator first learning of the event, e-mail the AE CRF to [REDACTED]; and
2. The reviewing IRB – As soon as possible, but no later than 10 working days after the investigator first learns of the event, report per the IRB's instructions.

The sponsor will conduct an evaluation of unanticipated adverse device effects. If the sponsor determines that an unanticipated adverse device effect presents an unreasonable risk to subjects, parts of the investigation presenting risks will be terminated. Termination will occur no later than 5 working days after the sponsor makes such a determination and no later than 15 working days after the sponsor first received notice of the effect.

11 STATISTICAL CONSIDERATIONS

11.1 HYPOTHESES AND SAMPLE SIZE CALCULATION

11.1.1 SAMPLE SIZE FOR THE PRIMARY EFFECTIVENESS ENDPOINTS

First Primary Effectiveness Endpoint

The first primary effectiveness endpoint is the reduction in the unmedicated diurnal IOP from baseline to 12 months postoperatively. The study objective is to show that the mean unmedicated diurnal IOP reduction of the study treatment (i.e. ab-interno transluminal viscoelastic delivery and trabeculotomy performed with OMNI system performed after uneventful cataract extraction) is superior to that of the cataract extraction alone. Based on recent approved MIGS studies, the mean \pm SD unmedicated diurnal IOP reduction at 12 months for the cataract extraction alone is 6.7 mmHg \pm 3.6 mmHg (N = 118) for Glaukos P170043 and 6.3 mmHg \pm 4.0 mmHg (N = 187) for Ivantis P160024. Therefore, the mean \pm SD unmedicated diurnal IOP reduction at 12 months for the cataract extraction alone is estimated as 6.5 mmHg \pm 3.8 mmHg.

The corresponding statistical hypotheses are as follows:

$H_0: \mu_{OMNI} \leq 6.5$ mmHg and $H_a: \mu_{OMNI} > 6.5$ mmHg, where μ_{OMNI} is the mean unmedicated diurnal IOP reduction at 12 months for the OMNI Surgical System in combination with Cataract Extraction.

Based on a one-sample t-test with a one-sided significance level of 0.025 (or two-sided 0.05), a sample size of 116 eyes at 12 months provides a statistical power of 80% at a true μ_{OMNI} of 7.5 mmHg.

Second Primary Effectiveness Endpoint

The second primary effectiveness endpoint is the reduction in the number of IOP-lowering medications from screening to 12 months (before medications washed out if applicable) postoperatively.

The study objective is to show that the mean reduction in number of IOP-lowering medications of the study treatment at 12 months is not inferior to that of the cataract extraction alone. Based on P170043 and P160024, the mean \pm SD of reduction in number of IOP-lowering medications at 12 months for the cataract surgery alone is 0.9 ± 0.8 and 1.1 ± 1.1 , respectively. Therefore, the mean \pm SD of reduction in the number of IOP-lowering medications at 12 months for the cataract surgery alone is estimated as 1.0 ± 1.0 . A non-inferiority margin of 0.25 is considered. Therefore, a difference between the mean reduction in number of IOP-lowering medications for the cataract alone (1.0) and the mean reduction in number of IOP-lowering medications for the study treatment (MOMNI), $1.0 - M_{OMNI}$, of < 0.25 indicates that the study treatment is not inferior to the cataract alone in reducing the number of IOP-lowering medications.

The corresponding statistical hypotheses are as follows:

$H_0: M_{OMNI} \leq 0.75$ and $H_a: M_{OMNI} > 0.75$ (i.e. $1.0 - M_{OMNI} < 0.25$).

Based on a one-sample t-test with a one-sided significance level of 0.025 (or two-sided 0.05), a sample size of 101 eyes at 12 months provides a statistical power of 80% at a true M_{OMNI} of 1.0 medication.

Sample Size for the Primary Effectiveness Endpoints

Both of the alternative hypotheses of the two primary effectiveness endpoints need to be achieved in order to prove the study treatment effect, so the significance level adjustment for the multiplicity is not performed for the primary effectiveness endpoints. Therefore, based on the two primary effectiveness endpoints discussed above, a sample size of 116 eyes at 12 months is needed. Considering a drop-out rate of about 10%, approximately 130 eyes should be enrolled and treated with the study treatment.

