2 STUDY OBJECTIVE

The objective of this study is to prospectively assess the impact of ab-interno transluminal viscoelastic delivery and trabeculotomy performed using the OMNI Surgical System in combination with cataract extraction on intraocular pressure (IOP) and the use of IOP-lowering medications in patients with mild to moderate open angle glaucoma (OAG).

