6 STUDY DESIGN

This is a prospective, multicenter, single-arm, post-market study.

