11.4.1 PRIMARY EFFECTIVENESS ENDPOINTS

The IOP reduction from baseline to 12 months postoperatively and the reduction in number of IOP-lowering medications from baseline to 12 months will be calculated for each eye and summarized descriptively. The 95% confidence interval of the mean reduction will be derived based on the t-distribution. The one-sample t-test will be performed for testing the statistical hypotheses described in Section 11.1.1. It should be noted that, for eyes with secondary surgical interventions (SSI) to control IOP or with SSI that can affect the IOP before 12 months, the last available observed data before the SSI will be used to impute the 12-month data. For the analyses based on the mITT population, the following imputation for subjects with missing 12-month data but without SSI may be performed:

- The within-eye worst IOP (collected after 3 months postoperatively or IOP at baseline for the subjects with no data after postoperative 3 months) for the missing 12-month IOP and worst number of IOP lowering medications (collected after 3 months postoperatively or IOP-lowering medication data at baseline for the subjects with no data after postoperative 3 months) for the missing 12-month number of IOP-lowering medications.
- The worst IOP (collected after 3 months postoperatively or IOP at baseline for the subjects with no data after postoperative 3 months) during the study for the missing 12-month IOP and worst number of IOP-lowering medications (collected after 3 months postoperatively or IOP-lowering medication data at baseline for the subjects with no data after postoperative 3 months) during the study for the missing 12-month number of IOP-lowering medications.
- The mean IOP during the study for the missing 12-month IOP and mean number of IOP-lowering medications during the study for the missing 12-month number of IOP-lowering medications.
- The last-observed-carry-forward approach.

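### The first primary objective claims superiority to cataract extraction alone, but the one-sample test takes the historical 6.5 mmHg as known, so its 2.5% error and 80% power do not apply to that claim

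*Combined protocol and SAP*

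**What the plan says.** Section 6 describes the design: "This is a prospective, multicenter, single-arm, post-market study". Section 2 is modest: "The objective of this study is to prospectively assess the impact". The comparative claim enters in Section 11.1.1, where the aim for the first primary endpoint is to show that the mean reduction in unmedicated diurnal IOP "is superior to that of the cataract extraction alone".

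The comparator comes from two earlier device studies, whose cataract-only groups had mean reductions of 6.7 ± 3.6 mmHg (N = 118) and 6.3 ± 4.0 mmHg (N = 187). The plan averages them and says that the mean reduction "for the cataract extraction alone is estimated as 6.5 mmHg", with SD 3.8. The null hypothesis is a mean of at most 6.5 mmHg in the treated eyes. The test is a one-sample t-test at one-sided 0.025, with 116 eyes for 80% power at a true mean of 7.5 mmHg.

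The second primary endpoint follows the same pattern. The cataract-alone reduction is estimated as 1.0 medication, and a shortfall below 0.25 "indicates that the study treatment is not inferior to the cataract alone in reducing the number of IOP-lowering medications". Both alternative hypotheses "need to be achieved in order to prove the study treatment effect".

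Section 11.4.1 carries this through: "The one-sample t-test will be performed for testing the statistical hypotheses described in Section 11.1.1". The only interval planned for these endpoints is for the treated eyes: "The 95% confidence interval of the mean reduction will be derived based on the t-distribution".

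**The concern.** The hypothesis as written compares one mean with a constant. The objective compares two treatments, one of them known only through 305 historical eyes. The plan itself calls 6.5 an estimate but then gives it no error. It does not name 6.5 a performance goal, and no planned output shows the uncertainty of the difference from cataract extraction alone.

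A significant result would support a mean reduction above 6.5 mmHg. Read through the stated objective, it would be reported as superiority to cataract extraction alone at a 2.5% error rate that was never established for that claim. Some results would pass the planned test even though a 95% confidence interval for the difference from the historical groups still includes zero.

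**Working it through.** **Inputs (Section 11.1.1).** n = 116, SD 3.8 mmHg, one-sided 0.025, benchmark 6.5, design mean 7.5; historical groups 6.7 ± 3.6 (N = 118) and 6.3 ± 4.0 (N = 187).

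**1. The plan's own figure.** The one-sample t-test power from the noncentral t, for a difference of 1.0, is 80.25% at n = 116 and 79.9% at n = 115. The stated 116 reproduces exactly.

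**2. Standard errors.**
- This trial: 3.8/√116 = 0.353.
- Historical simple average, as the plan forms it: 0.5 × √(3.6²/118 + 4.0²/187) = 0.5 × √(0.1098 + 0.0856) = 0.221.
- Difference: √(0.353² + 0.221²) = 0.416.

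**3. Pass thresholds at an observed SD of 3.8.**
- Planned test: 6.5 + 1.981 × 0.353 = 7.20 mmHg.
- 95% interval for the difference (Welch-Satterthwaite df 209, t = 1.971): 6.5 + 1.971 × 0.416 = 7.32 mmHg.

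An observed mean between 7.20 and 7.32 passes the first and not the second. The chance of landing there is 10.9% at a true mean of 7.5 and 1.4% at 6.5.

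**4. Error and power for the superiority claim.** The condition is that the historical groups and this study share one true cataract-alone mean. The planned rule is averaged over historical sampling error with standard deviation 0.221. Power is at a true difference of 1.0 mmHg.

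| SD | One-sided error | Power |
|---|---|---|
| 3.6 | 5.1% | 80.0% |
| 3.8 | 4.8% | 76.5% |
| 4.0 | 4.6% | 73.0% |

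These powers belong to a rule with inflated error. The figure comparable with the planned 80% is the power of a test that uses the combined standard error and holds 2.5%. At n = 116 and SD 3.8 it is 66.7%, and it reaches 80% only at a true difference of 1.17 mmHg. For 80% power at 1.0 mmHg, the normal approximation needs 3.8²/[(1/2.802)² − 0.221²] ≈ 184 evaluable eyes, where 2.802 = 1.960 + 0.842.

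**5. Error at a fixed true cataract-alone mean, if the device adds nothing.** It is 0.6% at 6.3, 2.5% at 6.5 and 8.1% at 6.7 mmHg. The outer values are the two source means.

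**6. Sensitivity to how the two groups are combined.** The benchmark stays at 6.5, with n = 116 and SD 3.8.

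| Weighting | Historical mean | Averaged error | Interval threshold | Chance of the disputed band at 7.5 |
|---|---|---|---|---|
| Simple average (the plan's) | 6.50 | 4.8% | 7.32 | 10.9% |
| Inverse variance | 6.475 | 4.2% | 7.29 | 8.3% |
| By N | 6.455 | 3.8% | 7.27 | 6.5% |

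The N-weighted mean is (118 × 6.7 + 187 × 6.3)/305 = 6.455.

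**Medication endpoint.** The structure is the same, but Section 11.1.1 prints no group sizes beside the historical medication figures, so I give no size for it.

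**The case against.** A fixed benchmark is a legitimate single-arm design. The plan prints its sources, states its hypotheses openly, and ties alpha and power to a one-sample test at a true treated mean of 7.5 mmHg. On that reading nothing is miscalculated, and what remains is one loosely worded objective and its counterpart for medications. That is correct about the arithmetic and is why the tests and the 116 can stay. It does not remove the problem, because the plan presents these hypotheses as the ones that correspond to a superiority objective, and that link is what fails.

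The size is also open to argument. The disputed zone is only 0.08 to 0.12 mmHg wide, and the error falls below 2.5% if the true cataract-alone mean is under 6.5. Under other weightings the averaged error is 3.8% to 4.2% rather than 4.8%. All of this stands. The 4.8% follows from the plan's own simple average and is the largest of the three. The roughly 67% power of a test that holds 2.5% hardly depends on the weighting.

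Finally, an added interval does not reach the larger threat, which is differences between trial populations, and it could invite the comparative reading it is meant to temper. The first part is true, and the documents give no means of quantifying those differences. The interval therefore needs its limitation stated beside it.

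**Conclusion.** The concern holds. The planned test is valid for a mean reduction above 6.5 mmHg, but the stated objective goes further than the test supports. With sampling error alone and a shared cataract-alone mean, the one-sided error for the superiority claim is about 4.8% on the plan's simple average (3.8% to 4.2% under the other weightings), against a nominal 2.5%. Power at an error rate that does hold is about 67%, against a nominal 80%. Differences in population, sites or period between the historical studies and this one are not included.

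This should be corrected, because the wording determines what a positive result will be said to show. It does not call the sample size for the written IOP hypothesis into question.

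**What to change.** Keep the primary tests and the sample size, and make two changes.

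1. **Section 11.1.1, wording.** Restate the first objective as showing that the mean unmedicated diurnal IOP reduction with the study treatment exceeds a fixed performance goal of 6.5 mmHg, derived from historical cataract-extraction-alone results. Restate the second in the same way with a goal of 0.75 medications, and amend the non-inferiority sentence to match. State that 2.5% and 80% refer to these goals, and that neither superiority nor non-inferiority to cataract extraction alone is concluded from these tests alone.

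2. **Section 11.4.1, one prespecified sensitivity analysis for IOP.** Use the same populations and imputation as the primary analysis. Report the observed treated mean minus 6.5 mmHg, with standard error √(s²/n + 0.221²), where 0.221 = 0.5 × √(3.6²/118 + 4.0²/187), and a 95% interval with Welch-Satterthwaite degrees of freedom. State beside it that it covers sampling error only, not differences between trial populations.

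Section 11.1.2 builds its 73% and 55% benchmarks in the same way, though without claiming superiority. Describing them as performance goals too would keep the sections consistent.

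The cost is a protocol and SAP amendment, with sponsor approval and IRB review as necessary under Section 14, and a few lines of code using numbers already printed. No extra patients are needed. The price to the sponsor is a weaker headline claim.

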11.1.2 SAMPLE SIZE FOR THE SECONDARY EFFECTIVENESS ENDPOINT

The first secondary effectiveness endpoint is the 12-month outcome of $\geq 20\%$ reduction in unmedicated diurnal IOP (medication washed out if applicable) from baseline. Based on P170043 and P160024, the percent of eyes achieving this outcome for the cataract surgery alone is 75.4% (89/118) and 70.1% (131/187). Therefore, the percent of cataract-surgery-alone eyes achieving this secondary effectiveness outcome is estimated as 73%. The corresponding statistical hypotheses are $H_0: P_{1\text{OMNI}} \leq 0.73$ and $H_a: P_{1\text{OMNI}} > 0.73$, where $P_{1\text{OMNI}}$ is the probability of eyes achieving the first secondary effectiveness endpoint.

The second secondary effectiveness endpoint is the 12-month outcome of unmedicated diurnal IOP (medication washed out if applicable) of ≥ 6 mmHg and ≤ 18 mmHg. Based on P170043 and P160024, the percent of eyes achieving this outcome for the cataract surgery alone is 63.6% (75/118) and 47.6% (89/187). Therefore, the percent of cataract-surgery-alone eyes achieving this secondary effectiveness outcome is estimated as 55% (approximate average of 63.6% and 47.6%). The corresponding statistical hypotheses are $H_0: P_{2\text{OMNI}} \leq 0.55$ and $H_a: P_{2\text{OMNI}} > 0.55$, where $P_{2\text{OMNI}}$ is the probability of eyes achieving the second secondary effectiveness endpoint.

The formal conclusion of the secondary effectiveness endpoints will not be determined if the primary effectiveness endpoints are not statistically significant. Meanwhile, the conclusion of the second secondary effectiveness endpoint will not be determined if the first secondary effectiveness endpoint is not statistically significant (i.e., using the step-down approach for the secondary effectiveness endpoint). Therefore the significance level is two-sided 0.05 or one-sided 0.025 for both of the secondary effectiveness endpoints.

Based on the binomial distribution with a one-sided significance level of 0.025 (or two-sided 0.05), a sample size of **105** eyes at 12 months provides a statistical power of at least 80% at a true $P_{1\text{OMNI}}$ of 0.85, and a sample size of **91** eyes at 12 month provides at least 80% at a true $P_{2\text{OMNI}}$ of 0.70. Therefore, at least **105** eyes at 12 months are needed for the secondary effectiveness endpoints.

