11.1.3 SAMPLE SIZE OF THE STUDY

Based on the discussion in Section 11.1.1 and 11.1.2 the sample size for the effectiveness endpoints is **130** eyes treated with the study device with the cataract surgery.

With a sample size of 130 eyes, there is a probability of 95% to observe at least one incidence of a safety event with an event rate of about 2.4%.

In May of 2019, the study protocol was revised to require at least one ocular hypotensive medication at the screening for the study eyes. Since the study has treated

some eyes that did not have ocular hypotensive medications at screening, the planned sample size of the study is increased to approximately 145 eyes.

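### The 101 eyes stated for the medication co-primary do not give 80% power at one-sided 0.025: they give 70.1% at the printed SD of 1.0, which needs 128 eyes

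*Combined protocol and SAP*

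**What the plan says.** Section 11.1.1 sizes the two co-primary endpoints separately.

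- **Medications.** The null is a mean reduction of 0.75 or less (1.0 for cataract surgery alone, less a margin of 0.25), and the assumed true value is 1.0. The two source studies report 0.9 ± 0.8 and 1.1 ± 1.1, and the value "for the cataract surgery alone is estimated as 1.0 ± 1.0". The calculation is introduced with "Based on a one-sample t-test with a one-sided significance level of 0.025 (or two-sided 0.05"), and the result is that "a sample size of 101 eyes at 12 months provides a statistical power of 80% at a true" mean of 1.0.
- **IOP.** With a null of 6.5 mmHg, a true mean of 7.5 mmHg and an SD of 3.8 mmHg, "a sample size of 116 eyes at 12 months provides a statistical power of 80"%.
- **Combined.** Both endpoints must succeed, so the larger requirement is carried forward: "a sample size of 116 eyes at 12 months is needed". Then: "Considering a drop-out rate of about 10%, approximately 130 eyes should be enrolled and treated with the study treatment".

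Section 11.1.3 repeats 130 as the effectiveness sample size and raises the total to about 145, because some treated eyes had no medication at screening.

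**The concern.** The null, the alternative, the test, the significance level and an SD are all printed, so the 101 can be checked directly, and it fails. Both co-primaries must be met to show a treatment effect, and Section 11.1.2 allows no formal conclusion on the secondary endpoints otherwise. The planned power of the medication endpoint therefore matters for the whole confirmatory sequence. If its true requirement is above 116, the statement that 116 evaluable eyes suffice is also wrong, and medications rather than IOP set the study size. From the plan as written a reader cannot tell which case applies.

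**Working it through.** **Inputs** (Section 11.1.1): difference 1.0 − 0.75 = 0.25 medications; one-sided α = 0.025; target power 80%; planning SD 1.0; source SDs 0.8 (N = 118) and 1.1 (N = 187). The plan gives no separate SD for the study treatment.

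**Formula.** Exact one-sample t-test power is 1 − F(t₀.₉₇₅,ₙ₋₁), where F is the noncentral t distribution with n − 1 degrees of freedom and noncentrality λ = difference × √n / SD.

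**Check of the method on the plan's other figures.**

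- IOP, difference 1.0 and SD 3.8: power is 79.9% at n = 115 and 80.3% at n = 116. The plan's 116 reproduces.
- First secondary endpoint, exact binomial, 0.73 against 0.85: 79.1% at 104 and 84.7% at 105. The plan's 105 reproduces.
- Second secondary endpoint, 0.55 against 0.70: 79.1% at 90 and 83.2% at 91. The plan's 91 reproduces.

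**Medication endpoint at the printed SD of 1.0.** For n = 101, λ = 0.25 × √101 / 1.0 = 2.51, and power is 70.1%. Power is 79.8% at n = 127 and 80.2% at n = 128, so 128 eyes are needed.

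**Other SDs that the plan prints or that follow from its two sources** (one-sided 0.025, difference 0.25):

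| SD | Origin | Power at 101 | Power at 116 | N for 80% |
|---|---|---|---|---|
| 0.80 | first source | 87.5% | 91.6% | 83 |
| 0.95 | (0.8 + 1.1)/2 | 74.5% | 80.3% | 116 |
| 0.962 | root mean square | 73.5% | 79.3% | 119 |
| 0.984 | N-weighted average | 71.5% | 77.5% | 124 |
| 0.995 | pooled, √[(117 × 0.8² + 186 × 1.1²)/303] | 70.6% | 76.5% | 127 |
| 1.00 | printed planning value | 70.1% | 76.1% | 128 |
| 1.10 | second source | 61.9% | 68.0% | 154 |

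None gives 101. A normal approximation does not explain it either: it needs 126 eyes at SD 1.0 and 114 at SD 0.95.

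**What would give 101.** Three settings do: one-sided α = 0.05 with SD 1.0 (79.9% at 100, 80.2% at 101); 70% power at one-sided 0.025 with SD 1.0; or an SD of about 0.884 to 0.888 at one-sided 0.025. The first two contradict the stated level or power, and the third SD appears nowhere. The documents do not show which, if any, was used.

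**Does it reach 116 and 130?** The plan's other planning values sit at or near simple averages: IOP SD (3.6 + 4.0)/2 = 3.8; 73% from (75.4 + 70.1)/2 = 72.75; 55% as the "approximate average of 63.6% and 47.6"%, which is 55.6. The same rule gives 0.95 here. Then 0.25/0.95 = 0.263 = 1/3.8, the same standardised effect as IOP, so each co-primary separately needs 116.

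After 10% dropout, 130 treated eyes leave 130 × 0.9 = 117. Power for medications at 117 is 80.6% at SD 0.95 and 76.5% at SD 1.0. At SD 1.0, 80% needs 128/0.9 = 142.2, so 143 eligible treated eyes.

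**The case against.** The strongest reply is that 101 drives nothing. The plan carries 116 forward, and no enrolment target, test, margin, population or decision rule uses 101. If the SD is 0.95, correcting it changes no other number. If the SD is 1.0, the loss at 116 eyes is about 4 percentage points, and a true mean of 1.013 instead of 1.0 would bring power back to 80.2%. This stands, and it limits the consequence, but it does not make the stated power correct.

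A second reply is that the printed SD of 1.0 describes cataract surgery alone and the power sentence names no SD. That is so, but the IOP figure reproduces with the borrowed control SD of 3.8, so borrowing is evidently the plan's practice. In any case no SD derived from the sources gives 101.

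Third, 0.95 is an inference. The plan prints 1.0, and the averaging is only approximate (55.6 became 55). This is fair: 70.1% and 128 follow from the printed inputs, while 74.5% and 116 depend on the sponsor confirming the unrounded average.

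Finally, 145 exceeds 143. That does not help, because the increase from 130 compensates for treated eyes without screening medication, and Section 11.2 excludes those eyes from the mITT and PP populations.

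**Conclusion.** The concern holds. At the stated one-sided 0.025, 101 eyes give 70.1% power at the printed SD and 74.5% at SD 0.95, not 80%. The figure understates the requirement by 128 − 101 = 27 eyes or 116 − 101 = 15 eyes respectively.

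Whether anything else is affected depends on the SD. At 0.95, the 116 evaluable and 130 treated eyes are enough for each co-primary taken separately. At 1.0, the medication endpoint has the larger requirement, and its power is 76.1% at 116 evaluable eyes.

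These figures assume the plan's true mean of 1.0, an SD borrowed from cataract surgery alone, and about 10% dropout. They are powers for one endpoint at a time; the plan makes no claim about joint power. The error concerns planned power only, is small in practice, and should be corrected because the endpoint is mandatory for success.

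**What to change.** In Section 11.1.1, state the SD used for the medication endpoint and replace 101 with the number it gives at one-sided 0.025.

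- **If SD 0.95 is confirmed:** print it unrounded and change 101 to 116. The 116 and 130 stand.
- **If SD 1.0 is kept:** change 101 to 128. Say in Section 11.1.1 that medications have the larger requirement and that 116 evaluable eyes give 80% power for IOP but about 76% for medications. Say in Section 11.1.3, where the text reads "Based on the discussion in Section 11.1.1 and 11.1.2 the sample size for the effectiveness endpoints is" 130, that 130 treated eyes (about 117 evaluable) give about 76.5% for medications, and that 80% would need about 143 eligible treated eyes.
- **If another SD was used:** print it with its source.

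The correction itself requires no extra enrolment. With SD 1.0, leaving enrolment unchanged means accepting about 76% power for this endpoint, and the plan should say so openly. The cost is one N and one SD, plus two sentences if 1.0 is kept. No data collection or analysis changes.

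### Both co-primaries must be met, but 116 eyes is the 80% size for IOP alone; joint power is not stated and is about 61% at the printed planning values if the endpoints are independent.

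*Combined protocol and SAP*

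**What the plan says.** Section 11.1.1 sizes the two primary endpoints one at a time.

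- **IOP reduction.** The null value is 6.5 mmHg and the SD 3.8 mmHg. The test is a one-sample t-test at one-sided 0.025. The plan says of its figure of 116 that it "provides a statistical power of 80% at a true μ_{OMNI} of 7.5 mmHg".
- **Reduction in medications.** The reference mean and SD for "the cataract surgery alone is estimated as 1.0 ± 1.0". With a margin of 0.25, the null value is 0.75. The plan gives 101 eyes for 80% power at a true reduction of 1.0, with the same test and alpha.

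It then sets the success rule: "Both of the alternative hypotheses of the two primary effectiveness endpoints need to be achieved in order to prove the study treatment effect". This rule is used to explain why alpha is not adjusted. The sizing conclusion comes straight after it: "Therefore, based on the two primary effectiveness endpoints discussed above, a sample size of 116 eyes at 12 months is needed". Adding about 10% drop-out gives 130 treated eyes. No joint power and no correlation between the endpoints is stated.

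Section 11.1.2 gates the secondaries: "The formal conclusion of the secondary effectiveness endpoints will not be determined if the primary effectiveness endpoints are not statistically significant". The second secondary also waits on the first. Power of at least 80% is given for each secondary test, at 105 eyes (0.73 against 0.85) and 91 eyes (0.55 against 0.70).

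Section 11.1.3 raises the planned total to about 145, because some eyes had been treated without any hypotensive medication at screening. Section 11.2 leaves those eyes out of the mITT and PP populations.

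**The concern.** A rule that requires both tests to succeed has two consequences. Each test can be run at full alpha, and the chance of success falls below the power of the weaker test unless the two outcomes are almost perfectly dependent. The plan draws the first consequence and not the second. Taking the larger of two single-endpoint sizes protects each test separately; it does not size the trial for winning both.

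At stake is how the result will be read. Someone planning around this trial, or interpreting a failure on one endpoint, would look for the probability of meeting the trial's own success rule and find only single-test figures. The same holds for the secondaries, whose printed powers do not reflect the gate in front of them. Type I error is not affected.

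**Working it through.** **Inputs (11.1.1).** One-sample t-test, one-sided alpha 0.025. IOP: difference from null 7.5 − 6.5 = 1.0, SD 3.8. Medications: difference 1.0 − 0.75 = 0.25, SD 1.0. n = 116.

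**Formula.** Power = P(T > t₀.₉₇₅,ₙ₋₁), where T is noncentral t with n − 1 degrees of freedom and noncentrality (difference/SD)·√n. At n = 116 the critical value is 1.981.

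**Step 1: reproduce the plan's figures.**
- IOP: noncentrality (1.0/3.8)·√116 = 2.834, power 80.3%. At n = 115 power is 79.9%, so 116 is the smallest size reaching 80%. It reproduces exactly.
- Medications at n = 101: power 70.1%, not 80%. The printed inputs need 128 eyes (80.2%; 127 gives 79.8%). The figure of 101 is obtained with an SD of about 0.89 at one-sided 0.025, or with SD 1.0 at one-sided 0.05 (80.2%). The documents do not show which was used.

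**Step 2: medication power at n = 116.**
- SD 1.0: noncentrality 0.25·√116 = 2.693, power 76.1%.
- SD 0.89: noncentrality 0.25·√116/0.89 = 3.025, power 85.1%.

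**Step 3: joint power at n = 116.** Under independence it is p₁·p₂. Otherwise the two test statistics are treated as bivariate normal with the correlation shown. The bounds are p₁ + p₂ − 1 and min(p₁, p₂).

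| Correlation | SD 1.0 (printed) | SD 0.89 (101 eyes accepted) |
|---|---|---|
| 0 | 0.803 × 0.761 = 61% | 0.803 × 0.851 = 68% |
| 0.5 | 66% | 72% |
| 0.8 | 71% | 76% |
| Lower bound | 0.803 + 0.761 − 1 = 56% | 0.803 + 0.851 − 1 = 65% |
| Upper bound | 76% | 80% |

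For scale, 80% joint power under independence would need 159 eyes at 12 months (SD 1.0) or 142 (SD 0.89).

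**Step 4: secondaries.** The stand-alone figures reproduce by exact binomial calculation:
- 105 eyes, success at 86 or more responders: alpha 0.0226, power 84.7%.
- 91 eyes, success at 60 or more: alpha 0.0223, power 83.2%.

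At n = 116 they are 85.6% and 91.1%. A formal secondary conclusion also requires both primaries, so its probability cannot exceed joint primary power: at most 76.1% on the printed inputs, or 80.3% if 101 is accepted. A simulation at n = 116 on the printed inputs, with assumed endpoint correlations (0 to 0.5 between the primaries, 0 to 0.8 between IOP reduction and the latent secondary response), gave about 53–61% for the first secondary and 48–59% for the second.

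**Step 5: the increase to 145.** If every one of the 145 eyes counted and 10% dropped out, about 130 would remain (145 × 0.9 = 130.5). Joint power under independence would be 68% (SD 1.0) or 75% (SD 0.89). This is a favourable reading, since the increase offsets eyes that 11.2 excludes.

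**The case against.** The strongest reply is that the plan nowhere promises 80% for the pair. It attaches 80% to each endpoint at a stated true value of that endpoint, and 116 is correct for the test it belongs to. That stands: a reader might infer from the sizing sentence that 80% is the chance of trial success, but the text does not say so. The fault is an operating characteristic left unstated, not a miscalculation of 116.

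A reader might also infer that the gate makes the printed secondary powers wrong, or that the secondaries can never reach 80%. Neither is supported. The 105- and 91-eye figures are correct as stand-alone powers. A ceiling below 80% is strict only at SD 1.0 with 116 eyes; if 101 is accepted the ceiling is 80.3%, though that needs near-perfect correlation.

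Third, the shortfall depends on a conservative alternative. A true medication reduction of 1.0 assumes no advantage over cataract surgery alone. At SD 1.0 and n = 116, a true reduction of 1.10 gives medication power of 96% and independent joint power of 77%; at 1.25 the joint figure is 80.2%. The small six-month series in Section 5 report falls from 2.8 to 0.4 and from 2.7 to 1.1 medications. They are weak evidence, but they point above 1.0. This also stands, so the figures must be tied to the planning alternatives. It does not excuse the omission, because the plan's own 80% figures rest on those same alternatives.

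**Conclusion.** The point holds as a gap in the power statement. Section 11.1.1 calls the IOP-only 80% size the number needed for a pair of endpoints that must both succeed. At the planning alternatives and printed SDs, 116 eyes give about 61% joint power under independence and no more than 76% at any correlation. Accepting the 101-eye figure, joint power is about 68% under independence and at most 80%.

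It would go too far to say that the trial's chance of success is 61–68%. Both ends assume independence, which the documents do not state. Both are conditional on true effects of 7.5 mmHg and 1.0 medication. The gap between them comes from the unresolved conflict between 101 eyes and an SD of 1.0, which is a separate error. The SD of 0.89 is printed nowhere; it is back-calculated, and one-sided 0.05 would explain 101 equally well. The conclusion that joint power falls short of 80% at realistic correlations holds on either SD. The increase to 145 does not clearly cure it.

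**What to change.** Keep the sample size, tests, alpha and decision rule.

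1. In 11.1.1, first reconcile the 101-eye medication figure with SD 1.0, which needs 128 eyes at one-sided 0.025. Either correct the number or state the SD or alpha that produced it.
2. Then state in 11.1.1 that 116 eyes give 80% power for the IOP endpoint alone, and add the joint power for both co-primaries at the planning alternatives, with the correlation assumed and the range over correlations. On the printed inputs that is about 61% under independence, 66% at correlation 0.5, range 56–76%.
3. In 11.1.2, label the 105- and 91-eye figures as stand-alone test powers, and say that the chance of a formal secondary conclusion is capped by joint primary power (at most 76% on the printed inputs at 116 eyes).

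The cost is a few sentences and a less favourable stated figure. No extra patients are needed.
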